### 2.7 ADMINISTRATION OF TRIAL MEDICATION

IMP will be taken once daily during both parts of the study. IMP doses are fixed and will not be adjusted for individual subjects during the study.

At each visit (where appropriate, see Section 8.7 of the protocol) subjects will be dispensed IMP for self-administration for daily dosing until the subsequent visit, with overage included to allow for visit windows. An interim check of compliance will be made at all study visits (as appropriate).

Page 12 of 50

Statistical Analysis Plan Final V1.0, 14 Mar 2024

NeRRe Therapeutics Ltd Protocol: ORV-PF-01

Subjects will be required to take one tablet of IMP once-daily in the evening before retiring to bed. The study medication may be taken with or without food.

### 2.7.1 Missed dose

All doses are to be taken at approximately the same time each evening. If a subject forgets to take a dose in the evening it may be taken any time up until 9 am the following morning. After this time the dose should not be taken and it will be considered a missed dose.

### 2.7.2 Dose interruption

If a subject experiences an AE which the investigator believes is treatment related and which the subject finds intolerable, a break in dosing of up to 1 week is permitted. If on reintroduction of the IMP the AE recurs and remains intolerable the IMP will then be withdrawn altogether. A break in dosing will not result in extension of the overall dosing period.

Page 13 of 50

Statistical Analysis Plan Final V1.0, 14 Mar 2024

# 2.8 SCHEDULE OF ASSESSMENTS AND PROCEDURES

Table 1: Schedule of Events

Table 1: Schedule of Events								
	Screening Visit	Baseline	Treatment Period A	t Period A	End of Wash- Out / Start of	Treatmen	Freatment Period B	Follow-up/ Early
			Week 2 f	Week 4	Period B	Week 2f	Week 4	Termination b
Visit (V) Number	1	7	3	†	2	9	7	&
Timing of visit	Within 14 to 28 days of V2	Day 0	14 days after V2	28 days after V2	21 days after V4	14 days after V5	28 days after V5	14 days after V7
Allowable window	N/A	0	±3 days	±3 days	±3 days	±3 days	±3 days	±3 days
Informed Consent a	X							
Medical History & demographics	X							
Physical examination	X	οX						Xc
Pulmonary function tests (spirometry)	íΧ	X		X	X		X	X
Inclusion/exclusion criteria	X	${}_{ m p}{ m X}$						
Concomitant medication review	X							XX
Vital signs e	X	X		X	X		X	X
12-lead ECG	X	X		X	X		X	X
AE recording		X						XX
Issue eDiary/Training/Compliance check	X	X	X	X	X	X		
Randomisation		X						
eDiary completion (once daily) i	X						X	
Study drug dispensing/training		X			X			
Study drug collection/compliance check				X			X	
Ambulatory cough monitoring		X		X			X	
Daily dosing (evening before bed)			X h	X		X h	X	
Leicester Cough Questionnaire		X		X	X		X	
Hull Airway Reflex Questionnaire		X		X			X	
K-BILD Questionnaire		X		X	X		X	
PROMIS SF SD 8b		X		X	X		X	
Hospital Anxiety and Depression Scale		X		X	X		X	
Global ratings of status/change in cough		Xg	X	X	X	X	X	X
Biomarker samples		X		X	X		X	
Clinical chemistry and haematology	X	X		X	X		X	X
Blood sample for orvepitant concentration				X	X		X	
Urinalysis	X	X		X	X		X	X

### 3 ENDPOINTS

### 3.1 PRIMARY EFFICACY ENDPOINT AND ESTIMAND

The primary endpoint is the mean change from baseline to Week 4 (the last 7 days of treatment) in weekly average of the daily IPF coughing severity scale score. The coughing severity scale is an 11-point numerical rating scale (NRS) that is completed daily by patients in an electronic diary.

### 3.1.1 ESTIMAND

### 3.1.1.1 Primary Estimand

The primary estimand includes the following attributes:

- Treatment of interest: Orvepitant (10 mg or 30 mg once daily) compared to placebo.
- Population of interest: Patients with IPF and troublesome chronic cough in whom the cough is attributed to the IPF, regardless of whether or not they receive prohibited medications during treatment or have other protocol violations.
- Variable / endpoint of interest: Change from baseline to Week 4 in weekly average (the average of the last 7 days before the relevant visit) of the daily IPF coughing severity scale score.
- Potential intercurrent events/Strategy to address:
  - o Initiation of concomitant medications or withdrawal from study treatment: A treatment policy strategy will be used, essentially following the intention to treat principle. Any patients who discontinue treatment early will be followed up until the end of the study, with the aim of collecting all scheduled data.
  - Death during the study: A while on-treatment strategy will be used. All data for any subjects who died will be included up to the point of their death and no imputation will be made for any visits that were scheduled to have occurred after the date of death.
- Population-level summary: Difference in mean change from baseline to Week 4 in weekly average of the daily IPF coughing severity scale score between orvepitant (10 mg or 30 mg once daily) compared to placebo.

This estimand targets the effect of treatment on the variable measurement regardless of adherence to the treatment or the protocol. The primary analysis is to be done on the FAS and is expected to be sufficient for analysis of this estimand.

### 3.1.1.2 Supportive Estimand

The supportive estimand is cough severity in patients with IPF.

• Treatment of interest: Orvepitant (10 mg or 30 mg once daily) compared to placebo.

- Population of interest: Patients with IPF and troublesome chronic cough in whom the cough is attributed to the IPF, with no protocol violations which potentially confound the analysis of the primary efficacy endpoint.
- Variable / endpoint of interest: Change from baseline to Week 4 in weekly average (the
  average of last 7 days before the relevant visit) of the daily IPF coughing severity scale
  score.
- Potential intercurrent events: Subjects with intercurrent events that are considered protocol
  violations (e.g. prohibited concomitant medication) that may affect the primary efficacy
  analysis will have data excluded from the analysis. For other intercurrent events a similar
  strategy as for the primary estimand will be used.
- Population-level summary: Difference in mean change from baseline to Week 4 in weekly average of the daily IPF coughing severity scale score between orvepitant (10 mg or 30 mg once daily) compared to placebo.

This estimand targets the effect of treatment on the variable measurement in the target population in which intercurrent events which potentially confound the analysis of the primary efficacy endpoint did not occur. The primary analysis is to be repeated on the Per Protocol Set (PPS) and is expected to be sufficient for analysis of this estimand.

### 3.2 SECONDARY EFFICACY ENDPOINTS

The secondary efficacy endpoints comprise the following:

Assessment	Secondary Efficacy Endpoints
IPF coughing severity scale	Mean change from baseline to Week 2 in weekly average of the daily IPF coughing severity scale
Early morning coughing scale	Mean change from baseline to Weeks 2 and 4 in weekly average of the daily early morning coughing scale
Rest of the day coughing scale	Mean change from baseline to Weeks 2 and 4 in weekly average of the daily rest of the day coughing scale
Urge to cough scale	Mean change from baseline to Weeks 2 and 4 in weekly average of the daily urge to cough scale
Dyspnoea scale	Mean change from baseline to Weeks 2 and 4 in weekly average of the daily dyspnoea scale
Cough frequency scale	Mean change from baseline to Weeks 2 and 4 in weekly average of the daily cough frequency scale
Patient global ratings of status for all coughing, early morning	Proportion of subjects in each category at Weeks 2 and 4

coughing and rest of the day	
Patient global ratings of change for all coughing, early morning coughing and rest of the day	Proportion of subjects in each category at Weeks 2 and 4
coughing  Cough frequency measured using the Leicester Cough  Monitor ambulatory cough monitor	
 
Mean change from baseline to Week 4 in 24-hour cough frequency
 
Mean change from baseline to Week 4 in awake cough frequency
 

	Mean change from baseline to Week 4 in night-time cough frequency
	Mean change from baseline to Week 4 in the number of coughing bouts
Leicester Cough Questionnaire (LCQ)	Mean change from baseline to Week 4 in LCQ total and domain (Physical, Social, Psychological) scores
King's Brief Interstitial Lung Disease health status questionnaire (K-BILD)	Mean change from baseline to Week 4 in K-BILD total and domain (Psychological, Breathlessness and Chest Symptoms) scores
	Proportion of patients with a clinically relevant improvement in total K-BILD score
PROMIS SF SD 8b sleep assessment questionnaire	Mean change from baseline to Week 4 in the PROMIS SF SD 8b score
Hospital Anxiety and Depression Scale (HADS) questionnaire	Mean change from baseline to Week 4 in the HADS score
Hull Airway Reflux Questionnaire (HARQ)	Mean change from baseline to Week 4 in HARQ score

# 3.3 EXPLORATORY ENDPOINTS

The following exploratory endpoints will be assessed:

Assessment	Endpoint
Plasma/serum biomarkers	Mean change from baseline in the concentration of plasma/serum markers of inflammation and fibrosis

Plasma concentrations of orvepitant measured in spot samples	
 
PK exposure-response relationship for the orvepitant group will be carried out to examine the possible relationship between clinical efficacy and plasma levels of the drug
 

--	---

# 3.4 SAFETY ENDPOINTS

The safety endpoints comprise the following:

Assessments	Safety endpoints	
Pulmonary function tests measured using a spirometer	Change from baseline to each post-baseline assessment time-point in forced vital capacity (FVC), forced expired volume in one second (FEV1), peak expiratory flow rate and vital capacity (VC)	
Adverse events recorded	Number of treatment emergent adverse events	
throughout the study	Number of treatment emergent serious adverse events	
	Number of treatment emergent adverse events resulting in treatment discontinuation	
	Severity of treatment emergent adverse events	
	Number of treatment emergent related adverse events	
Physical Examination	Treatment emergent changes in physical examination will be recorded as adverse events	
Vital Signs (pulse rate, systolic and diastolic blood pressure, arterial oxygen saturation, temperature, weight).	Mean change from baseline to each post-baseline assessment time-point in each vital sign:     Systolic blood pressure     Diastolic blood pressure     Pulse rate     Temperature     Arterial oxygen saturation     Weight     Clinically significant changes in vital signs are recorded as adverse events	

Page 19 of 50

Haematology, clinical chemistry and urinalysis parameters	
 
Mean change from baseline to each post-baseline assessment time-point in each haematology parameter
 
	
	Mean change from baseline to each post-baseline assessment time-point in each clinical chemistry parameter	
	Shift from baseline to each post-baseline assessment time-point in each urinalysis parameter	
	Clinically significant changes in laboratory parameters are recorded as adverse events	
12-lead ECG parameters	Proportion of subjects with clinically significant abnormal ECG findings at each post-baseline assessment time-point	
	Proportion of subjects with non-significant abnormal findings at each post-baseline assessment time-point	
	Change from baseline to each post-baseline assessment time-point in ECG intervals:	
	
 
PR
 
QT, QTc and QTcF
 
RR
 
Proportion of subjects at each post-baseline assessment time-point with maximum absolute QTcF values by category
 
	
	
 
≤450, >450 to ≤480, >480 to ≤500, >500 msec
 
Proportion of subjects at each post-baseline assessment time-point with maximum change from baseline in QTcF values by category
 
	
	
 
≤0, >0 to ≤30, >30 to ≤60, >60 msec
 
Clinically significant changes in ECG findings are recorded as adverse events
 
	

### 4 ANALYSIS POPULATIONS

# 4.1 SAFETY SET (SS)

All subjects who receive at least one dose of double-blind study drug irrespective of treatment received. Subjects will be analysed according to treatment received.

Statistical Analysis Plan Final V1.0, 14 Mar 2024

NeRRe Therapeutics Ltd Protocol: ORV-PF-01

### 4.2 FULL ANALYSIS SET (FAS)

All randomised subjects who received at least one dose of double-blind study drug, irrespective of treatment received, and have sufficient IPF coughing severity scale data for at least one post-treatment assessment. Subjects will be analysed according to randomised treatment. This set will be used for the primary efficacy analysis.

### 4.3 PER PROTOCOL SET (PPS)

All subjects in the FAS excluding those identified as having a relevant protocol violation, where a relevant violation is one that potentially confounds the analysis of the primary efficacy endpoint.

In addition, subjects who experience a respiratory adverse event that may result in a change in coughing status and that coincides with one or other of the evaluation periods will be excluded from the PPS.

Analysis Sets will be agreed at a blinded data review meeting (BDRM) prior to the unblinding of the study.

### 4.4 PROTOCOL DEVIATIONS

Protocol deviations must be documented in the subject's medical notes, in the electronic case report form, and/or clinical trial management system.

Prior to database lock, NeRRe will be responsible for producing the final protocol deviation listing (formatted as a Microsoft Excel file), in collaboration with the listing will be by subject and will include a description of the protocol deviation/violation, the occurrence date, the categorisation as major / minor and the categorisation as relevant / not relevant. Deviations classified as relevant will result in exclusion of the subject from the PPS. This file will be finalised and signed prior to database lock, at a BDRM.

A listing of all protocol deviations by subject and deviation category will be provided, indicating which are relevant deviations as determined before unblinding.

### 5 GENERAL ASPECTS FOR STATISTICAL ANALYSES

### 5.1 GENERAL METHODS

- All analyses and summaries will be produced using SAS® version 9.4 (or higher).
- All analysis will be analysed by cohort such that there will be two placebo groups presented unless specified otherwise.
- Categorical variables will be summarised using the number of observations (n), frequency and
  percentage of subjects. All percentages will be presented as one-decimal point, unless
  otherwise specified. Percentages equal to 100 will be presented as 100% and percentages will
  not be presented for zero frequencies.
- If log transformation is to be applied prior to analysis, a positive constant (1) will be added in cases of zero value prior to transformation. Analysis results will be back transformed to the original scale for reporting.
- Continuous variables and ordered categorical data will be summarised using the number of subjects with evaluable data, mean, standard deviation (SD), geometric mean (where

Page 21 of 50

Statistical Analysis Plan Final V1.0, 14 Mar 2024

NeRRe Therapeutics Ltd Protocol: ORV-PF-01

appropriate), median, first and third quartiles, minimum and maximum. In case of 0 values where geometric mean is calculated, 1 is added to every number in the data set, and then subtracted from the resulting geometric mean. The same number of decimal places as in the raw data will be presented when reporting minimum and maximum, 1 more decimal place than in the raw data will be presented when reporting the mean and median, and 2 more decimal places than in the raw data will be presented when reporting the SD. For ordered categorical data and nominal data, absolute counts and relative frequencies (in %) will be calculated.

- Lower and upper bound values for the confidence intervals (CIs) will be reported to 2 more decimal places than the raw data.
- All statistical hypothesis tests and CIs will be two sided, using a type I error rate of 0.05.
- Unless stated otherwise, the percentages will be based on the number of non-missing observations. The column header will still contain the number of subjects in the treatment group. There will be a row for the number of non-missing observations in the table (at each time point, if required) for each variable being summarised.
- Any calculated p-values will be presented to 3 decimal places; p-values less than 0.001 will be presented as 'p<0.001' and p-values greater than 0.999 will be presented as 'p>0.999'.
- All relevant subject data will be included in listings and sorted by treatment group, Subject ID, and visit, as applicable, for all randomised subjects.
- Unscheduled or repeat assessments will not be included in summary tables unless specified. All assessments will be included in the subject listings.
- All tables, listings and figures will include footers that identify the name of the program that created the output, together with the date and time on which it was created. Headers will include the total number of pages that the presentation contains and, for each page, the number of the page within the presentation.

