Study medication compliance for Treatment Period B will be checked during the visit. The medication bottle will be returned to the patient so that they can take the last dose the same evening, with the medication being finally returned to the site at the same time and using the same method as for the ACM. Compliance will be checked again when the bottle is returned.

8.7.8 Visit 8

Visit 8 is the follow up / early termination visit for the study. It should be scheduled for 14 (± 3) days after Visit 7 or at the earliest opportunity if the subject withdraws early.

The following assessments and procedures will be undertaken at the clinic site or during a home visit:

- Vital signs
- Symptom directed physical examination
- Spirometry
- 12-lead ECG
- Safety labs: blood samples for clinical chemistry and hematology and urine sample for urinalysis
- Global ratings of cough status and change
- A review of changes in concomitant medications and any changes in health status (AEs)

Protocol No.: ORV-PF-01 Final V4.0 (US) Page 38 of 85

9. INVESTIGATIONAL PRODUCT AND ADMINISTRATION

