### **5.3.2** Visit Windowing

For summaries of by visit safety data, the CRF visit will be used. Unscheduled visits will be listed but not mapped to a specific analysis visit.

For summaries and analyses of efficacy data, the following table outlines the analysis visits that efficacy data will be mapped to. Efficacy assessments will be mapped to a study analysis visit as long as the study day(s) falls within the windows specified in Column A (Protocol allowed window for the visit) or Column B (Reasonable limits for out of window days for actual visit to be associated with nominal Visit). Efficacy data collected on days falling out of analysis visit windows (Column C) will be reviewed at the BDRM and may be assigned to an analysis visit window if appropriate.

Study Analysis Visit	Target Day for CRF Visit	A. Protocol allowed window for the visit (inclusive)	B. Reasonable limits for out of window days for actual Visit to be associated with nominal Visit	C. Unaccounted for days
Baseline (Visit 2)	0	N/A	N/A	N/A
Treatment Period A - Week 2 (Visit 3)	14	11 to 17	7ª to 10 18 - 20	1 to 6
Treatment Period A - Week 4 (Visit 4)	28	25 to 31	21 to 24 32 to 34 b	35 to 39
[Wash-out start]	29	N/A	N/A	N/A
End of Wash- Out / Start of Period B (Visit 5)	B0° [49]	N/A [46 to 52]	N/A [42 to 55]	N/A
Treatment Period B - Week 2 (Visit 6)	B14 [63]	B11 to B17 [60 to 66]	B7 a to B10 [56 to 59] B18 to B20 [67 to 69]	B1 to B6
Treatment Period B - Week 4 (Visit 7)	B28 [77]	B25 to B31 [74 to 80]	B21 to B24 [70 to 73] B32 to B34 b [81 to 83]	B35 to B39

a. Earliest day on which a 7 day data collection period is possible

The weekly average score is derived using scores recorded in the eDiary from the last 7 calendar days up to and including the date of the relevant visit (as defined in the visit window above).

Page 24 of 50

b. Last day a fully compliant subject will be able to dose (subjects are provided with 34 days of study medication)

c. Please note that for the purposes of visit window assignment only the clock is re-set for treatment period B

[] = nominal study day, where Baseline Visit 2 = Day 0; BDRM = blinded data review meeting

At least 4 scores are required to derive a weekly average. These four scores do not have to be on consecutive days. If 4 scores are not recorded in the eDiary the weekly average will be considered missing for that visit.

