### 8.4 ECG DATA

ECGs will be assessed by the investigator for overall abnormal findings and will be classified as Normal, Abnormal not clinically significant or Abnormal clinically significant. These will be summarised by the proportion of subjects within each category at each post-baseline assessment by treatment group. Shift tables will also be presented.

The actual value and change from period-specific baseline (see Section 5.2.2) will be summarised descriptively by treatment group and time point for each ECG interval parameters by treatment group.

- **ECG** intervals:
  - ORS duration

- PR
- QT, QTc and QTcF
- RR

QTcF interval will be derived using: QT interval/(RR interval)^1/3

In addition, the proportion of subjects at each post baseline assessment with maximum absolute QTcF values by the following categories will be presented:

- <450 msec
- >450 to <480 msec
- >480 to <500 msec
- >500 msec

Similarly, the proportion of subjects at each post baseline assessment with increase from baseline in QTcF values by the following categories will be presented:

- <0 msec
- >0 to <30 msec
- >30 to <60 msec
- >60 msec

All ECG parameters will be listed.

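### The maximum-QTcF tables leave out unscheduled and repeat ECGs, and early-termination ECG and laboratory values have no rule assigning them to a treatment

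*SAP*

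**What the plan says.** Four rules act together.

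- **General exclusion.** SAP 5.1: "Unscheduled or repeat assessments will not be included in summary tables unless specified". The same bullet adds "All assessments will be included in the subject listings", and the bullet before it has listings "All relevant subject data will be included in listings and sorted by treatment group, Subject ID, and visit".
- **Visit assignment.** SAP 5.3.2: "For summaries of by visit safety data, the CRF visit will be used", and "Unscheduled visits will be listed but not mapped to a specific analysis visit".
- **QTcF categories.** SAP 8.4 plans "the proportion of subjects at each post baseline assessment with maximum absolute QTcF values" in four bands, with a matching table for the increase from baseline. Protocol 8.3 and SAP 3.4 word the endpoints the same way, by time-point. Nothing in SAP 8.4 brings unscheduled or repeat ECGs back in.
- **Early termination.** Protocol 8.7.8: "Visit 8 is the follow up / early termination visit for the study". Protocol 7.4 gives subjects who withdraw after randomisation the Visit 8 procedures. Footnote b to the Schedule of Events allows that visit up to 14 days after termination or after stopping study drug.

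SAP 8.1 has an attribution rule for adverse events: those starting in the wash-out go to the Period A treatment, and those from the first Period B dose through follow-up go to the Period B treatment. There is no equivalent rule for ECG or laboratory values.

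**The concern.** A table of maximum QTcF exists to show the worst reading a subject had on each treatment. Unscheduled and repeat ECGs are often taken because something looked abnormal, so they are a likely place for that reading to occur. Under the stated rules it could not enter the table.

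The early-termination gap works in the same direction. A subject who leaves because of a problem may have the last near-treatment ECG and blood sample at a visit that carries the Follow-up number. If those values are summarised with Follow-up, they sit beside readings from completers who have cleared the drug.

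Safety is one of the two primary objectives (Protocol 6.1), and its analysis is purely descriptive (SAP 8). The tables are therefore the main by-treatment comparison with placebo that a reader will see.

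**Working it through.** No figure in the plan needs reproducing. The check traces the rules and then sizes the consequences.

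**Step 1: scheduled on-drug ECGs.** Protocol 10.2.4 schedules ECGs at Visits 1, 2, 4, 5, 7 and 8. Visits 1 and 2 precede dosing. Visit 5 ends the wash-out, and Visit 8 follows Visit 7 by 14 days. That leaves Visit 4 in Period A and Visit 7 in Period B: one on-drug ECG visit per treatment period. Protocol 10.2.4 describes no replicate tracings. If one tracing is recorded per visit, the maximum at a visit is simply that reading. If several were recorded, it would be the maximum at that visit, still not over the period.

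**Step 2: how much drug remains.** With the stated half-life of about 33 hours (Protocol 11.2, SAP 2.6.4) and simple exponential decline, residual fraction = 0.5^(24 × days / 33).

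| Days after last dose | Half-lives | Residual |
|---|---|---|
| 1 | 0.73 | 60% |
| 3 | 2.18 | 22% |
| 7 | 5.09 | 2.9% |
| 11 (earliest in-window Visit 8) | 8.0 | 0.39% |
| 14 (nominal Visit 8) | 10.2 | 0.09% |
| 18 (earliest in-window Visit 5) | 13.1 | 0.01% |
| 21 (nominal Visit 5) | 15.3 | 0.003% |

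The visit rows count from Visit 4 or 7, when the last dose is due that evening. Visit 5 and a completer's Visit 8 are essentially drug-free. An early-termination value may be anywhere from on-drug to drug-free.

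**Step 3: where a high unscheduled reading goes.** Take a repeat ECG in Period A with QTcF above 480 msec, higher than the Visit 4 reading, judged not clinically significant.
- QTcF category tables: excluded (SAP 5.1, with no exception in 8.4).
- Normal/abnormal ECG table: also built by post-baseline assessment, so excluded.
- TEAE tables: not entered, because only clinically significant changes become adverse events.
- Listings: present.

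**Step 4: where an early withdrawer's values go.** Someone leaving before Visit 4 or 7 has no Week 4 value. SAP 5.1 bases percentages on non-missing observations, so that subject leaves both numerator and denominator of the Week 4 row. The values at the termination visit follow the CRF visit. If that is Visit 8, they fall in the Follow-up row, under a treatment column the SAP does not define.

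**Step 5: size.** Protocol 7.1 plans about 88 subjects in two equal cohorts: 88 / 2 = 44. One subject is 1 / 44 = 2.3% of a column. The documents give no rate for excursions seen only off schedule. For an assumed rate q per subject, the chance of at least one among 44 is 1 − (1 − q)^44:
- q = 0.5%: 20%
- q = 1%: 36%
- q = 2%: 59%
- q = 5%: 90%

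These rates are assumptions, shown only for range.

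**The case against.** A reader might infer more than the documents support.

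- **That the worst values appear under no treatment at all.** They do appear. Every assessment is listed by treatment group, out-of-range laboratory values are flagged and separately listed (SAP 8.2), and clinically significant ECG and laboratory changes become adverse events tabulated by treatment (SAP 3.4 and 8.1). A QTcF above 500 msec judged clinically significant would be in the TEAE tables.
- **That worst-case laboratory tables are incomplete.** None is planned. SAP 8.2 gives by-visit descriptives and shifts, as the protocol endpoints do, and limiting those to scheduled values is ordinary practice.
- **That the QTcF display departs from its endpoint.** It does not: Protocol 8.3 also defines the categories by time-point.
- **That early-termination values are certainly filed under Follow-up, and are on-drug.** The first is inferred from the shared visit number and the CRF-visit rule; the eCRF and table specifications may separate them. The second holds only for some subjects. Those who stop only study drug are meant to stay on scheduled visits (Protocol 7.4).
- **That 88 − 2 × 37 = 14 subjects (16%) are affected.** That headroom covers every cause of non-evaluability, including missing diary data, and says nothing about unscheduled ECGs.

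These points narrow the concern and stand as far as they go. The DSMB protects subjects during the trial but does not change the reported tables. Listings do not give a rate against placebo, and the adverse-event route depends on the investigator's judgement. The numeric QTcF categories do not, which is their purpose.

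**Conclusion.** The point holds in limited form. Followed exactly, the SAP can leave a subject's highest on-drug QTcF out of every QTcF summary table, including the one labelled maximum. It also leaves undefined the treatment under which an early withdrawer's ECG and laboratory values are summarised.

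The size is unknown: each subject missed is 2.3% of a 44-subject cohort, and the number missed could be zero. Efficacy conclusions are untouched. This is a cheap improvement to reporting, not a flaw that invalidates the safety analysis.

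The QTcF conclusion rests on there being no exception elsewhere in table specifications that were not available. The remark that the maximum equals a single reading assumes one tracing per scheduled visit. The pooling of termination with Follow-up values assumes that the eCRF uses one Visit 8 label for both.

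**What to change.** In SAP 8.4, use the exception that 5.1 allows and add a table for each treatment period of maximum post-dose QTcF and maximum increase from that period's baseline, in the existing categories.

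- **Include** scheduled, repeat, unscheduled and early-termination ECGs, assigned by date to the treatment received.
- **Window:** from the period's first dose to a stated cut-off after the last dose, for example 7 days (about 5 half-lives). A window running to the next period's first dose or to the end of follow-up would count Visit 5 and a completer's Visit 8 as on-drug, which step 2 shows they are not.
- **By-visit tables:** keep them on scheduled values, and show early-termination ECG and laboratory values in a separate row under the treatment last taken.
- **Optional:** a worst-case laboratory shift table on the same window. This would be an addition, not the correction of an existing table.

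The cost is a short SAP amendment and a few more tables, with no new data. On-treatment counts may look slightly less favourable. The rule should be fixed before unblinding.
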